The inconsistency of correct determination of body position of this accelerometer model when worn around the waist has been demonstrated by other authors (Berendsen et al., 2014, Hänggi et al., 2013). The inconsistency of correct identification of the sitting position in particular was highlighted by (Hänggi et al., 2013). Other researchers have investigated ways of improving the ability to correctly classify the sitting position (Skotte et al., 2014). The study by (Skotte et al., 2014)

determined that the addition of a second Actigraph GT3X accelerometer placed on the mid-thigh yielded excellent results in detection of the sitting position. Pressure sensors in subjects' hip pockets were used as a criterion measure to classify body position.

As mentioned previously, the feasibility undertaken by the CI determined that the ankle placement was superior to the waist for recognition of step count. When walking a ten metre distance with a walking aid, using observed step count as a criterion measure the ankle placement demonstrated a mean difference -1 step, (Limits of Agreement (LOA) +3 to -5 steps) compared to the waist placement (mean difference -7 steps, LOA +9 to -23 steps). These positive findings for step count for the ankle placement are supported by a recent study cited earlier using a similar Actigraph model investigating the accuracy of step count in older adults (Korpan et al., 2015).

Defining the research question

Using the findings from the feasibility study regarding the ankle placement of the Actigraph GT3X accelerometer and the research cited suggesting improved classification of the sitting position with the addition of a thigh mounted accelerometer the following research question is proposed:

Can an Actigraph GT3X accelerometer, placed at the ankle and thigh of the same leg, accurately measure body position and walking episodes undertaken by patients recovering from critical illness in a hospital ward?

A number of study objectives evolve from this research question, assisting in the development of the methodological processes required to answer it.

1. To determine the criterion validity of the ActiGraph GT3X accelerometer in detection of body position and step count when positioned either on the mid-thigh or ankle of the same leg.
2. To establish if there is a superior single body placement site (thigh or ankle) to objectively record body position and step count within this patient population.

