A sample size of 20 participants will be recruited. This sample size has been used in previous research investigating the validity of a different accelerometer model to quantify gait parameters in patients recovering from critical illness (Edbrooke et al., 2012). They predicted that 12 subjects were necessary based upon alpha = 0.05 (significance level), beta = 0.9 (power) and a correlation of $r = 0.75$, categorised as a good to excellent correlation (Trapp and Dawson, 2004). A sample size of 20 was also recruited in another study investigating the validity of accelerometer measurement within a hospitalised stroke population (Kramer et al., 2013). Recruiting a sample of 20 patients will permit some attrition should there be any accelerometer malfunction or decisions to withdraw, yet supply an achievable number for participant recruitment based on feedback from clinical colleagues working within the specialty.

Statistical analysis

IBM SPSS statistics (Version 20) will be used to undertake statistical analysis. Some data captured by the accelerometers is continuous and others categorical.

Categorical data

Categorical data, concerning body position (lying, sitting or standing) will be analysed using the Kappa statistic, calculating agreement between the accelerometer inclinometer data and direct observation. Each accelerometer placement site (thigh and ankle) will initially be analysed separately. Examination of the inclinometer raw data captured from both placement sites will determine whether an algorithm can be constructed using readings from both the ankle and thigh placement to improve determination of the sitting

position specifically if necessary. Direct observation will serve as the criterion measure for all the analyses.

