Percentage agreement of inclinometer raw data from the thigh and ankle accelerometers with direct observation for detection of each separate body position will be calculated. A further percentage agreement analysis will be undertaken if an algorithm can be constructed for determination of the sitting position using readings from both placement sites. This algorithm will be compared against direct observational raw data identifying the sitting position only. This result will be compared against the percentage agreement of the individual placement sites in determination of the sitting position. This will assist in determination of whether the algorithm is more superior to a single placement site in determination of the sitting position.

Continuous data

Agreement between step count recorded by each accelerometer placement site and direct observation (manual counts) as a criterion measure will be determined using Bland Altman analysis with 95% limits of agreement (LOA).

Acceptance of the devices over a three-hour period

The statements within the Likert scale will be collapsed to obtain true positives (very comfortable and somewhat comfortable) and true negatives (very uncomfortable and somewhat uncomfortable). The middle category (neither comfortable nor uncomfortable) will remain a separate category. A descriptive analysis will be undertaken to investigate this particular aspect of enquiry using percentages of true positives, the middle category and true negatives. This will be presented graphically.

Any specific comments made by the patients in relation to acceptability of the devices will be included as free text within the results section. The statements will be anonymous and permission from participants will be sought regarding their inclusion within the body of the thesis or publications which may arise from it.

Ethics approval

This study has received approval from the NHS Local Research Ethics Committee (REF: XXXXX) and the Research Ethics Sub Committee, YSJU (REF: XXXXXX).

Data handling and confidentiality

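### The only power calculation quoted for n = 20 concerns a correlation this study does not plan, so it says nothing about the precision of the kappa and limits-of-agreement results

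*Combined protocol and SAP*

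**What the plan says.** The section Sample size calculation opens with "A sample size of 20 participants will be recruited" and supports that number in four ways.

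- Precedent: "This sample size has been used in previous research investigating the validity of a different accelerometer model to quantify gait parameters" in survivors of critical illness.
- That study's own calculation, in which the assumed coefficient was 0.75: "They predicted that 12 subjects were necessary based upon alpha = 0.05 (significance level), beta = 0.9 (power) and a correlation of" that size. The protocol describes such a value as "categorised as a good to excellent correlation".
- A second precedent: an accelerometer validity study in hospitalised stroke patients that also recruited 20.
- Practicality: clinical colleagues regard 20 as achievable, and "Recruiting a sample of 20 patients will permit some attrition".

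The analyses appear under Statistical analysis. Body position "will be analysed using the Kappa statistic, calculating agreement between the accelerometer inclinometer data and direct observation", with percentage agreement for each position. Agreement between device and manual step counts "will be determined using Bland Altman analysis with 95% limits of agreement (LOA"). Comfort ratings are described by percentages. No correlation coefficient is planned. The section gives no target kappa, acceptable limit of agreement, target interval width, attrition rate or minimum number of analysable participants, and it asks for no confidence interval around any estimate.

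**The concern.** The cited calculation answers whether a correlation differs from zero. The study's objectives ask something else: criterion validity against observation, a step count comparable to the observer's, and which single site is better. These are questions of agreement. A device can track the observer closely in rank and slope and still be wrong by a large, consistent amount, so power for a correlation is no guide to how well agreement will be estimated.

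The remark that 20 leaves room for attrition has 12 as its only numerical reference point, and 12 has no meaning for kappa or limits of agreement. If losses are judged against it, the study could fall to 12 analysable participants and still look adequately sized. Because no intervals are requested, limits from 12 to 20 people could be read as firmer than they are when concluding on validity and on the better placement site.

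**Working it through.** **1. Reproduce the cited 12.** Inputs from Sample size calculation: alpha 0.05, power 0.9, r = 0.75. Sidedness and the null value are not stated; I take the null as zero. By Fisher z, n = ((z_alpha + z_power) / atanh(0.75))² + 3, with atanh(0.75) = 0.973.

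- One-sided: ((1.645 + 1.282) / 0.973)² + 3 = 12.05.
- Two-sided: ((1.960 + 1.282) / 0.973)² + 3 = 14.10.

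Simulating the t-test of r under bivariate normality gives power at n = 12 of 0.92 one-sided and 0.86 two-sided. The cited 12 is therefore roughly reproducible. The arithmetic is not the problem.

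**2. Correlation against agreement (assumed figures).** Suppose manual counts have mean 40 and SD 15, and a device records half of all steps plus noise of SD 3. Then r = 7.5 / √(7.5² + 3²) = 7.5 / 8.08 = 0.93, well above 0.75, while the bias is 20 − 40 = −20 steps.

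**3. Precision of a limit of agreement.** With one difference per participant, the 95% half-width for each limit is t(n−1, 0.975) × SD × √(1/n + 1.96² / (2(n−1))).

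- n = 20: 2.093 × √(0.0500 + 0.1011) = 2.093 × 0.389 = 0.81 SD.
- n = 12: 2.201 × √(0.0833 + 0.1746) = 2.201 × 0.508 = 1.12 SD.

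For the mean difference, t × SD / √n gives 2.093 / 4.472 = 0.47 SD at 20 and 2.201 / 3.464 = 0.64 SD at 12.

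**4. Illustration in steps.** The feasibility study, described just before Defining the research question, found for the ankle a "mean difference -1 step, (Limits of Agreement (LOA) +3 to -5 steps"). The limits span 8 steps, so SD = 8 / 3.92 = 2.04.

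- n = 20: 0.814 × 2.04 = 1.7 steps.
- n = 12: 1.118 × 2.04 = 2.3 steps.

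These limits lie 4 steps from the mean difference. They are reported in whole steps; if each is rounded by up to 0.5, the span is 7 to 9, the SD 1.79 to 2.30, and the half-width at n = 20 about 1.5 to 1.9 steps.

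**5. Kappa (illustrative range only).** The plan gives no within-participant structure. Two sets of assumptions give the scale.

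- Kappa 0.43 (the feasibility ankle value), three equally frequent positions (chance agreement 1/3), seven observations per participant, intraclass correlation (ICC) 0 to 0.5. Observed agreement is 0.43 × 2/3 + 1/3 = 0.62, and the half-width is 1.96 × √(0.62 × 0.38 / (n_eff × (2/3)²)), with n_eff = 7n / (1 + 6 × ICC). This gives 0.12 to 0.24 at n = 20 (n_eff 140 to 35) and 0.16 to 0.31 at n = 12 (n_eff 84 to 21).
- Kappa averaged over participants, between-participant SD 0.15 to 0.35, half-width t × SD / √n. This gives 0.07 to 0.16 at n = 20 and 0.10 to 0.22 at n = 12.

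The devices record every second (Study procedure). An interval that counted each second as independent would be far too narrow.

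**The case against.** The strongest reply is that the protocol claims little. The 0.9 power is reported as the earlier study's; this study states no power of its own. Its 20 also rests on two studies of similar size and on what can be recruited. It is a single-group, unfunded PhD validation study with no formal test or success threshold for power to govern, and the remedy leaves n unchanged. All of this stands, and it limits the point to the stated justification and the reporting of precision.

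Four stronger readings are tempting, and the documents do not support them.

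- A reader might infer that the study claims 90% power for itself. The sentence attributes the calculation to the earlier study.
- A reader might infer an assurance that 20 is more than adequate. The text says only that 20 allows some attrition and is achievable; 12 as a floor is implied, never stated.
- A reader might take ±1.7 steps as the precision this study will deliver. The SD comes from healthy volunteers simulating weakness over a fixed ten metres with a walking aid, whereas the Semi structured movement protocol lets each patient's ability set the distance. Only the multiples of SD carry over.
- A reader might set the kappa half-widths beside the feasibility gain from recoding the zero reading (0.48 − 0.43 = 0.05). That gain is a paired change on the same recordings, so the interval for a single kappa is not its uncertainty.

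It is also fair that missing confidence intervals are a reporting matter distinct from the sample-size basis. They belong together here because the intervals show what 20 participants can establish. Precedent and achievability do not show that.

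**Conclusion.** The point holds in a limited form. The only power calculation quoted does not apply to any planned analysis, and nothing in the plan replaces it with a target or expected precision. The size in transferable terms is ±0.81 SD for each limit of agreement with 20 analysable participants and ±1.12 SD with 12, a widening of 1.12 / 0.81 = 1.4 times. This assumes one step-count difference per participant and approximately normal differences. The step figures are illustrative, because the SD in patients walking distances of their own choosing is unknown. The kappa ranges rest wholly on assumptions that the plan does not supply. The planned estimates and n = 20 are not undermined. What changes is how firmly a study of this size can conclude on validity and on the better site.

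**What to change.** Keep n = 20. In Sample size calculation, remove the correlation as the basis (which also removes the labelling of power as beta) and retain precedent and achievability as the practical reasons. Then state the expected precision, for example: with one step-count difference per participant, each 95% limit of agreement will have a 95% confidence interval of about ±0.81 SD with 20 analysable participants, widening to ±1.12 SD with 12. If the feasibility SD is used to express this in steps, label it as an illustration from healthy volunteers over a fixed distance. Judge attrition against this precision.

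In Statistical analysis, add 95% confidence intervals for the mean difference and for each limit at each site. Add an interval for kappa that treats the participant as the unit, for example a bootstrap that resamples participants. State that each participant contributes one step-count difference; if several walks per participant are to be used, name a method that allows for repeated measures.

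The cost is one paragraph of wording and a few extra intervals, with no extra patients or procedures. The downside is a less favourable stated justification for the sample size.

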A feasibility study undertaken by the chief investigator (CI), as part of a PhD programme of study, determined that an ankle placement of the Actigraph GT3X accelerometer was superior to the waist for determination of body position and step count. In this study, thirty healthy adult volunteers simulated patients weakened by critical illness. They performed a movement protocol which incorporated the typical activities undertaken by patients recovering in hospital from critical illness. These included moving from lying to sitting, sitting to standing (and vice versa) and walking short distances. Video recordings were taken of each participant during the movement protocols, enabling observation of the body positions adopted and step counting during the walking activities. Video recording was used as the criterion measure for comparison against the data captured by the accelerometers worn both at the ankle and the waist. The activities detailed above are typically included within early mobility protocols which have undergone evaluation within populations experiencing critical illness (McWilliams et al., 2015, Adler and Malone, 2012, Schweickert et al., 2009). Moderate agreement ($\kappa = 0.43$, $p < 0.001$), was found between observation of video recordings of body position (lying, sitting or standing) and the inclinometer setting for the ankle placement. Fair agreement only ($\kappa = 0.21$, $p < 0.001$) was found for the waist placement. Regular misclassification of all body positions was found with the waist placement. The ankle placement identified both the lying and standing positions well. The sitting position however was only correctly identified intermittently for the ankle placement. A novel finding emerged from this research relating to the ankle placement site. When a side lying position was adopted, the ankle accelerometer inclinometer function regularly registered a '0'. The '0' setting normally corresponds to a 'not being worn' option. When a reading of '0' was recoded to the option 'side lying,' agreement improved from $\kappa = 0.43$ ($p < 0.001$) to $\kappa = 0.48$ ($p < 0.001$). This finding suggests a new way of interpreting the '0' reading of the inclinometer when worn on the ankle, which is worthy of further investigation within an actual patient population.

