3. To investigate the criterion validity of the combination of thigh and ankle accelerometer inclinometer outputs to correctly determine the sitting position. This

will determine whether an algorithm can be constructed using the two inclinometer readings, which will better distinguish the sitting from the standing position.

4. To evaluate, from a user perspective, the acceptability of these devices in relation to the placement sites used. This will be achieved by asking patients to score the answer to a particular question through the use of a Likert scale. The question is:
 - How would you rate the comfort of wearing the accelerometers?

In consideration of the results from the feasibility study undertaken by the CI and research using the addition of a thigh mounted accelerometer to identify the sitting position (Skotte et al., 2014), the following hypotheses can be constructed:

Hypotheses

1. An ankle mounted Actigraph GT3X accelerometer, will accurately identify both the lying and standing positions when compared with direct observation as a criterion measure.
2. An ankle mounted Actigraph GT3X accelerometer, will capture a step count comparable to that recorded by direct observation in a population resident on a hospital ward recovering from critical illness.
3. The combination of inclinometer outputs of both the thigh and ankle placement sites will permit development of an algorithm permitting the ability to better distinguish between the sitting and standing position.
4. The ankle and mid-thigh accelerometer placement sites will be well tolerated by patients recovering on a ward from critical illness.

Subject selection and involvement

The study will invite adult hospital ward patients recovering from critical illness to wear one Actigraph GT3X accelerometer on the antero-medial mid-thigh and another on the ankle, resting above the lateral malleolus of the same leg. The accelerometers will be worn for a period of time not exceeding three hours. Each device will be attached with a single patient use broad elastic belt, secured by Velcro fastening, using a standardised placement protocol. The non – dominant leg will be the preferred placement side.

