Following completion of the data collection period, the information captured by the accelerometers will be downloaded as soon as possible onto the laptop computer. The time when a movement commenced and ceased (with the addition of five seconds to accommodate accelerometer processing), will be noted by the CI. The type of movement and body positions adopted will also be documented (lying, sitting or standing). If the movement involves walking, the CI will count the number of steps undertaken manually, entering all of the above information onto a data collection sheet. The participant will not miss any refreshments, food or any investigations and they will also be encouraged to undertake usual daily activities, e.g. reading a paper or watching the television. If the participant requests some time alone, in the case of making a phone call for example, the CI will comply, but encourage the participant to remain in the same body position. If they were sitting in a chair for example, they would be encouraged to remain seated, agreeing a time for the CI to return (e.g. fifteen minutes). Should any procedures or personal cares be necessary, the CI will respect the need for privacy and dignity and leave until they are complete. The data captured by the accelerometers during these time periods will be excluded from data analysis, as there will be no criterion measure (observation) to compare accelerometer data against.

Observational data will be collected by the CI using a data collection form specifically designed for this purpose, which will be entered into an electronic format within the IBM SPSS statistics programme (version 20) for data analysis. The CI will undertake all data collection procedures and undertake statistical analysis.

Upon completion of the period of observation the accelerometers will be removed and the skin examined for one final time. Participants will be asked to rate their views on acceptability of wearing the accelerometers at the two placement sites. They will be asked to consider the question in relation to the individual placement sites and in combination. One question will be asked:

1. How would you rate the comfort of wearing the accelerometers?

[figure not shown]
Participants will be requested to match their answer to a statement on a five-point Likert Scale which will be printed on a sheet for them:

1. Very uncomfortable
2. Somewhat uncomfortable
3. Neither comfortable or uncomfortable
4. Somewhat comfortable

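### The three-position kappa depends on how long participants sit, so Hypothesis 1 should rest on position-specific ankle results that also expose sitting read as standing

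*Combined protocol and SAP*

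**What the plan says.** All references are to the combined protocol and SAP.

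- **Statistical analysis, Categorical data:** "Categorical data, concerning body position (lying, sitting or standing) will be analysed using the Kappa statistic". Each site is first analysed separately. The unit of analysis, the way participants are combined and any threshold for kappa are not stated.
- **Same subsection, next paragraph:** percentage agreement for the thigh and ankle devices "with direct observation for detection of each separate body position will be calculated". The denominator is not defined.
- **Hypotheses, item 1:** the ankle device "will accurately identify both the lying and standing positions" against direct observation. No figure for accuracy is set.
- **Background, feasibility study:** "The ankle placement identified both the lying and standing positions well", whereas sitting was recognised only some of the time. The ankle kappa was 0.43, and 0.48 once a reading of 0 was counted as side lying.
- **Study procedure, and Subject selection and involvement:** the epoch is one second. Order is free, rest is available on request, no time is set for any position, and the session may last up to three hours. Participants are not held to the listed movements: "they will also be encouraged to undertake usual daily activities, e.g. reading a paper or watching the television".

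**The concern.** Hypothesis 1 leaves sitting out, and the feasibility results explain why. A kappa over lying, sitting and standing brings the sitting errors back in. If the one-second epochs are the unit, those errors are weighted by the time spent sitting, which participants control. The same sensor could then look good in a sample that stays in bed and poor in one that sits in a chair.

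The position-specific agreement avoids that, but it may have a gap of its own. If it is the share of observed standing seconds that the device calls standing, it does not show how often the device says standing when the patient is sitting. A sensor that calls most sitting standing would still score well. At stake is whether Hypothesis 1 is declared supported for standing when most standing readings may be false.

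**Working it through.** **The plan's own figure.** The feasibility kappa of 0.43 cannot be rebuilt, because no cross-table or posture mix is given. What can be shown is that it does not identify lying and standing accuracy:

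- Every position 62% correct, equal thirds: kappa = (0.62 − 0.333)/(1 − 0.333) = 0.43.
- Lying and standing 95% correct, sitting 30%, about 55% of time sitting and the rest split equally: kappa is also 0.43.

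**Inputs, all assumed.** The documents describe accuracy in words only. I take lying and standing as 95% correct, with the 5% errors split evenly between the other two positions. Sitting is 30% correct, and the other 70% is read as standing. That destination fits Objective 3, which concerns telling sitting from standing. The 0 reading is left out of the model.

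**Formulas.** Kappa = (po − pe)/(1 − pe). Standing specificity = 1 − (non-standing seconds read as standing)/(all non-standing seconds). Standing PPV = (true standing readings)/(all standing readings).

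**Worked case, lying/sitting/standing 45/45/10** (shares of all observed time):

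| Observed | Read lying | Read sitting | Read standing | Total |
|---|---|---|---|---|
| Lying | 0.4275 | 0.01125 | 0.01125 | 0.45 |
| Sitting | 0 | 0.1350 | 0.3150 | 0.45 |
| Standing | 0.0025 | 0.0025 | 0.0950 | 0.10 |
| Total | 0.4300 | 0.14875 | 0.42125 | 1 |

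- po = 0.4275 + 0.1350 + 0.0950 = 0.6575
- pe = 0.45 × 0.4300 + 0.45 × 0.14875 + 0.10 × 0.42125 = 0.3026
- Kappa = (0.6575 − 0.3026)/(1 − 0.3026) = 0.51
- Standing sensitivity = 0.0950/0.10 = 0.95
- Standing specificity = 1 − (0.01125 + 0.3150)/0.90 = 0.64
- Standing PPV = 0.0950/0.42125 = 0.23
- Lying: sensitivity 0.95, specificity 1 − 0.0025/0.55 = 0.995

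**The same sensor under other mixes:**

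| Lying/sitting/standing | Kappa | Standing sensitivity | Standing specificity |
|---|---|---|---|
| 80/10/10 | 0.69 | 0.95 | 0.90 |
| 60/30/10 | 0.59 | 0.95 | 0.75 |
| 45/45/10 | 0.51 | 0.95 | 0.64 |
| 25/65/10 | 0.37 | 0.95 | 0.49 |
| 15/80/5 | 0.24 | 0.95 | 0.41 |

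Kappa falls as sitting time rises, although nothing about the sensor has changed. Sensitivity stays fixed. Specificity falls too, so it is not free of the mix. The row percentages are: 70% of observed sitting is read as standing in every line of the table.

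**Sensitivity to the assumptions.**

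- If sitting is 10% correct, kappa runs from 0.63 to 0.16 over these five mixes; if 50% correct, from 0.74 to 0.35.
- At 45/45/10, sitting 10% correct gives standing specificity 1 − (0.01125 + 0.405)/0.90 = 0.54 and PPV 0.095/0.51125 = 0.19. Sitting 50% correct gives 1 − (0.01125 + 0.225)/0.90 = 0.74 and 0.095/0.33125 = 0.29.
- If only half of the misread sitting goes to standing (30% case), specificity is 1 − (0.01125 + 0.1575)/0.90 = 0.81 and PPV 0.095/0.26375 = 0.36.

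**The case against.** The strongest reply is that the plan already handles this. Agreement for each position is promised directly after the kappa, and it separates lying and standing from sitting. A reader might infer that the plan cannot test Hypothesis 1, or that the hypothesis could be rejected because participants sat for long periods. The documents do not support that: nothing ties Hypothesis 1 to kappa, sets a kappa threshold or states a rejection rule. This stands.

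A reader might also infer that the new kappa will be read against 0.43 or 0.48. Those values appear only as background and no such comparison is planned. Nor is 0.43 proof of the sitting problem alone, since recoding the 0 reading as side lying moved it to 0.48. This stands too.

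Three further points are fair. First, the study seeks naturalistic conditions, so agreement under patients' actual mix is a legitimate quantity, and a kappa reweighted to equal thirds would be a preference rather than a requirement. Second, standing specificity depends on the mix as well (0.90 to 0.41 above), so sensitivity and specificity alone do not remove the problem. Third, the extreme mixes are unsupported, because participants are prompted towards the end to do any movement they missed; but prompting fixes no durations.

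The undefined denominator remains, as does the lack of any statement about which result bears on Hypothesis 1.

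**Conclusion.** The point holds in a limited form and is a cheap improvement. The three-position kappa moves with sitting time and should not serve as the evidence for Hypothesis 1. The planned position-specific agreement is the right kind of evidence. If its denominator is the observed position, it is sensitivity only: in the worked case standing scores 95%, yet specificity is about 0.64 and fewer than one in four standing readings is true. Seeing the false-standing rate could change the conclusion on standing. In the same case lying is hardly affected.

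These sizes rest on assumed accuracies, an assumed destination for misread sitting, an assumed mix and one-second epochs as the unit. The documents give none of the first three and do not confirm the fourth. The argument concerns the ankle and need not carry over to the thigh or to a combined algorithm.

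**What to change.** In Statistical analysis, Categorical data:

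1. Name position-specific ankle results as the evidence for Hypothesis 1.
2. Define them as sensitivity and specificity for lying and for standing, calculated within each participant and averaged with equal weight.
3. Because standing specificity also depends on the mix, add the cross-table of observed position by inclinometer reading, including 0, as row percentages. It should show the share of observed sitting that is read as standing.
4. Keep kappa as a descriptive summary, with the observed share of time lying, sitting and standing printed beside it.

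The cost is a few sentences and a few lines of analysis on data already being collected. The downside is that standing estimates rest on fewer seconds and will be less precise than a figure over all positions appears to be.
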